	study baseline urine is obtained
	E6. Pregnant women with known fetal congenital anomaly (e.g.,
	genetic abnormality or major congenital malformation)
	based on antenatal ultrasound;
	E7. Any rapidly progressing disease or immediately life-
	threatening illness, including acute hepatic failure, or
	respiratory failure
	E8. Medical condition or other factor that in the judgment of the
	investigator might affect ability to comply with procedures.
Study Duration	The duration of study participation for each enrolled patient is
	approximately 28 days.
Study Endpoints	Primary Endpoint:
	Number (and percentage) of patients in each study arm with
	favorable clinical outcomes* at the EOS visit
	*favorable clinical outcomes are defined as a clinical response of
	improvement ^a and/or cure ^b
	^a Clinical improvement is defined as 1) Resolution of cUTI signs
	and symptoms present at baseline, 2) Development of no new cUTI
	symptoms and/or 3) Avoidance of parenteral antibiotic therapy, in
	or out of hospital, at any time after randomization
	^b Clinical cure is resolution of all acute signs and symptoms of
	cUTI and improvement to such an extent that no further

Effective Date: 06/23/2023 Page **10** of **44**

	antimicrobial therapy (IV or oral) is required for the treatment of the cUTI
	Secondary Endpoints:
	 Number (and percentage) of patients in each arm with microbiological eradication** of all baseline pathogens at the EOS visit **microbiological eradication of all baseline pathogens is defined as an end of study quantitative urine culture that shows all uropathogens found at baseline are reduced to <10⁵ CFU/mL and all baseline pathogens are not detected by EOS urine PCR (Cq>33) Subjective measurement of Treating Investigator Satisfaction Score as evaluated by the questionnaire at EOS Turnaround Time (as measured in hours) of molecular diagnostic procedures compared to conventional diagnostics (time from collection of samples to complete identification of organism(s) and availability of antimicrobial susceptibility results)
	Overall agreeability between the diagnostic results generated by PCR versus C&S as assessed by discordant analysis
	 Safety: Assessments of safety will include the following: Clinical observations Vital sign measurements Laboratory tests Reported adverse events Assessment of Treatment Emergent Adverse Events (TEAE) at EOS

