4. STUDY OBJECTIVES AND ENDPOINTS

This investigation intends to verify the clinical utility of urine PCR testing by comparing the diagnostic and therapeutic values of molecular diagnostic methods to traditional urine C&S in management of cUTI in adults.

Table 2. Study Objectives and Endpoints

OBJECTIVES	ENDPOINTS		
Primary			
To evaluate patients' symptomatic responses following diagnosis and treatment based on the results of the molecular methods versus the those of conventional urine culture method	• Number (and percentage) of patients in each study arm with favorable clinical outcome* at the EOS visit *favorable clinical outcomes are defined as a clinical response of improvement and/or cure a Clinical improvement is defined as 1) Resolution of cUTI signs and symptoms present at baseline, 2) Development of no new cUTI symptoms and/or 3) Avoidance of parenteral antibiotic therapy, in or out of hospital, at any time after randomization b Clinical cure is resolution of all acute signs and symptoms of cUTI and improvement to such an extent that no further antimicrobial therapy (IV or oral) is required for the treatment of the cUTI		

UPH-STD-05-01 Version: 0

Effective Date: 06/23/2023 Page **14** of **44**

Advarra IRB Approved Version 0, Date: 12 May 2023 / Pro00071764

Secondary

- To determine the efficacy of antibiotic selection using molecular methods versus the conventional urine culture method
- To assess clinical utility of PCR results during the clinical-decision-making phase in patient care
- To compare the availability of the antimicrobial susceptibility information from molecular testing and conventional testing at the time of initial antimicrobial therapy
- To quantify the overall agreeability between the diagnostic results generated by PCR versus C&S

- Number (and percentage) of patients in each arm with microbiological eradication** of all baseline pathogens at the EOS visit
 - **microbiological eradication of all baseline pathogens is defined as an end of study quantitative urine culture that shows all uropathogens found at baseline are reduced to <10⁵ CFU/mL and all baseline pathogens are not detected by EOS urine PCR (Cq>33)
- Subjective measurement of Treating Investigator
 Satisfaction Score as evaluated by the questionnaire at EOS

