8.4. Visit 3 - End-of-Study (Day 28 ± 7)

EOS assessment should be performed in-person within the specified buffer period. The Investigator or delegate will perform/collect the following:

- Vital signs
- Physical examination (may be complete, targeted, or omitted; discretion of the Investigator)
- Record(s) of any adjunctive therapeutic procedures performed
- Record(s) of concomitant medications
- Assessment of clinical outcome(s)
- Record(s) of any AEs/SAEs

Urine specimens will be collected for microbiological evaluation. In case the result of urine specimen identifies an unsuccessful treatment, the patient may be followed-up to verify the final clinical outcome if deemed necessary by the treating Investigator.

When both the results of urine C&S and urine PCR become available, the treating Investigator will answer an evaluation questionnaire concerning his/her judgement of the diagnostic test and therapeutic value of urine PCR and urine C&S.

In case of clinical failure* as determined by treating Investigator at EOS, the patient's condition will be considered an AE and followed-up accordingly.

*Clinical failure is defined as a patient who has 1) on-going AE/SAE at EOS and/or 2) persistent cUTI symptoms and/or 3) developed new symptoms of cUTI.

UPH-STD-05-01 Version: 0

Effective Date: 06/23/2023 Page **22** of **44**

At the end of the study, the Investigator will complete the Study Exit Form present at the end of the eCRF portfolio. This form must also be completed in the event of premature termination of the patient's participation should they, the Investigator, or the Sponsor choose to discontinue their participation.

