11.3.2. Primary and Secondary Endpoints

The primary endpoint is the number (and percentage) of patients in each study arm with FCl at the EOS visit; this term is defined as a *clinical response of improvement* and/or *clinical cure*:

Clinical response of improvement is defined as:

1) Resolution of cUTI signs and symptoms present at baseline, and/or

UPH-STD-05-01 Version: 0

Effective Date: 06/23/2023 Page **28** of **44**

- 2) Development of no new cUTI symptoms, and/or
- 3) Avoidance of parenteral antibiotic therapy, in or out of hospital, at any time after randomization

Clinical cure is the resolution of all acute signs and symptoms of cUTI and improvement to such an extent that no further antimicrobial therapy (IV or oral) is required for the treatment of the cUTI

The secondary endpoints include:

- Number (and percentage) of patients in each arm with *microbiological eradication* of all baseline pathogens at the EOS visit; *microbiological eradication* of all baseline pathogens is defined as an end of study quantitative urine culture shows all uropathogens found at baseline are reduced to <10⁵ CFU/mL and all baseline pathogens are not detected by EOS urine PCR (Cq>33)
- Subjective measurement of Treating Investigator Satisfaction Score as evaluated by the questionnaire at EOS
- Turnaround Time (TAT: as measured in hours) of molecular diagnostic procedures compared to conventional diagnostics (time from collection of samples to complete identification of organism(s) and availability of antibiotic sensitivity results)
- Overall agreeability between the diagnostic results generated by PCR versus C&S as assessed by discordant analysis

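### As written in 11.3.2, avoiding parenteral antibiotics is enough for a favorable outcome, even in a patient whose persistent and new cUTI symptoms make them a clinical failure under 8.4

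*Combined protocol and SAP*

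**What the plan says.** The primary objective (section 4, Table 2) concerns patients' "symptomatic responses following diagnosis and treatment based on the results of the molecular methods" compared with conventional culture. The primary endpoint is the proportion with a favorable clinical outcome at EOS, meaning improvement and/or cure.

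Section 11.3.2 defines improvement by three items:

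1. "Resolution of cUTI signs and symptoms present at baseline, and/or"
2. "Development of no new cUTI symptoms, and/or"
3. "Avoidance of parenteral antibiotic therapy, in or out of hospital, at any time after randomization"

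Cure requires resolution of all acute signs and symptoms and "improvement to such an extent that no further antimicrobial therapy (IV or oral) is required for the treatment of the cUTI".

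The synopsis (2.1) and Table 2 punctuate the list differently, with a comma after item 1 and a single connective later: "2) Development of no new cUTI symptoms and/or 3) Avoidance of parenteral antibiotic therapy, in or out of hospital, at any time after randomization".

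Section 8.4 defines clinical failure as a patient who has "on-going AE/SAE at EOS and/or 2) persistent cUTI symptoms and/or 3) developed new symptoms of cUTI", and has that condition followed up as an AE. Appendix I repeats this failure definition. Its success option is symptom-based and accepts either complete resolution or significant improvement.

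**The concern.** With and/or after item 1 and again after item 2, the 11.3.2 list is an inclusive *or*. Item 3 is a statement about treatment, not about symptoms, and on this wording it is sufficient by itself. A patient with no symptomatic response therefore counts as unfavorable only if baseline symptoms persist, new symptoms appear and parenteral antibiotics are given.

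Two things are at stake. First, the same patient can be a primary-endpoint success in 11.3.2 and a clinical failure in 8.4. Second, if the list is applied as written, the favorable proportion mixes symptom response with route of treatment. A real difference in symptom response is then diluted whenever non-responders in the two arms are reclassified at similar rates. The trial is open-label, so the scoring rule should be settled before outcomes are seen.

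**Working it through.** **Logic.** Let R = baseline symptoms resolved, N = no new symptoms, A = no parenteral antibiotics, T = no further therapy required.

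- Improvement under 11.3.2 = R or N or A. Cure = R and T. Favorable = R or N or A, because cure already implies R.
- Of the 16 combinations of R, N, A and T, only the two with R = N = A = 0 are unfavorable, so 14 are favorable.
- Persistent or new symptoms (not R, or not N) occur in 12 combinations. All 12 are failures on symptoms under 8.4, and 12 − 2 = 10 of them are favorable under 11.3.2.
- The case R = 0, N = 0, A = 1 is favorable under the literal list. It is also favorable if the 2.1 and section 4 punctuation is read as (1 and 2) or 3. It is not favorable if the items are all joined by *and*, or if the list is read as 1 and (2 or 3).

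These are counts of logical cases, not proportions of patients.

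**The plan's own figure.** Inputs from the G*Power output in 11.1: one-tailed Fisher's exact test, α = 0.05, rates 0.70 and 0.80, 287 per arm. Power is the sum, over all pairs of arm counts that the test rejects, of the product of the two binomial probabilities. This gives 0.85132 at 287 per arm (0.84997 at 286) and an exact size of 0.0404 at a common rate of 0.80. The plan states 0.8513193 and 0.0404397, so its figures are reproduced.

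**Illustration of dilution.** Assume the planning rates are true symptom-response rates (R and N). Let s be the share of non-responders that the literal rule scores as favorable, equal in both arms. The observed rate is p + (1 − p)s, and the arm difference is multiplied by (1 − s). For s = 0.5: 0.70 + 0.30 × 0.5 = 0.85 and 0.80 + 0.20 × 0.5 = 0.90.

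| s | C&S vs PCR from 70/80 | Power, 287 per arm | C&S vs PCR from 75/85 | Power, 287 per arm |
|---|---|---|---|---|
| 0 | 70 vs 80 | 0.851 | 75 vs 85 | 0.898 |
| 0.25 | 77.5 vs 85 | 0.713 | 81.25 vs 88.75 | 0.781 |
| 0.5 | 85 vs 90 | 0.519 | 87.5 vs 92.5 | 0.590 |
| 0.75 | 92.5 vs 95 | 0.279 | 93.75 vs 96.25 | 0.316 |
| 0.9 | 97 vs 98 | 0.124 | 97.5 vs 98.5 | 0.131 |

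The right-hand columns use the 75% control rate in the text of 11.1 plus 10 points.

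The documents do not give s. There is a bound: a non-responder who avoids parenteral therapy is always favorable, so if a share x of non-responders receives it, s is at least 1 − x. The value s = 0.5 is therefore reached even if half of the non-responders get parenteral antibiotics. The documents do not give x either.

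**The case against.** **The endpoint may not be scored mechanically.** Section 8.4 calls for an investigator assessment of clinical outcome, and Appendix I offers symptom-based improvement, failure and indeterminate options. In practice this may soften the problem. But 11.3.2 does not refer to Appendix I for the primary endpoint, and 11.3.3 points only to the definition in the earlier sections. The objection does make the effect on the rate conditional: a reader might infer that the favorable rate will approach 100%, and the documents support that only if 11.3.2 is applied literally.

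**The other places are not rival primary-endpoint rules.** This largely stands. The 2.1 and section 4 wording can be read as the same inclusive list. The stated use of clinical failure in 8.4 is AE follow-up, which explains why on-going AEs are included. Appendix I supports a secondary endpoint. A reader might infer three competing definitions of the primary endpoint; the documents show one loose definition and two texts that contradict its result.

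**The power figures rest on an assumed s.** This also stands. The definition behind the literature range of 60% to 90% in 11.1 is not visible. If the planning rates already reflect the literal rule, power stays at 0.85. Unequal shares in the two arms could move the difference either way.

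**IV rescue.** A reader might infer that the cure definition is wrong because a patient who resolves after parenteral rescue still counts as favorable. The documents do not support that. Such a patient, with symptoms resolved, none new and no further therapy needed, is favorable under every reading of the connectives considered above. That fits an objective of symptomatic response assessed at EOS, and 8.3 permits IV antibiotics as ordinary care. Scoring rescue as failure is an estimand choice.

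**Conclusion.** The improvement definition in 11.3.2 is wrong as written. It makes avoidance of parenteral antibiotics sufficient for success, which conflicts with the symptomatic objective and with the failure definition in 8.4 and Appendix I, and no other section repairs it. This conclusion rests on the wording alone and needs no assumed rate.

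The size is illustrative. Power falls from 0.85 to 0.52 if 70% and 80% are true symptom-response rates, half of the non-responders in each arm are scored favorable, and 287 per arm are analysed. A reader might infer that the trial is underpowered; the documents do not establish that, because they give neither the share nor the definition behind the planning rates.

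**What to change.** - In 2.1, section 4 and 11.3.2, use one wording: a favorable outcome requires resolution of the baseline cUTI signs and symptoms **and** no new cUTI symptoms at EOS. Apply it to the favorable outcome as a whole, so that the cure route cannot bypass it.
- Take avoidance of parenteral therapy out of the *or* list, so that it cannot create a success by itself.
- Align 8.4 and Appendix I so that no patient is both favorable and a clinical failure on symptoms. Use one stated symptom threshold throughout; at present a much improved patient with residual symptoms fits both Appendix I options. State that an on-going AE alone does not determine the primary endpoint.
- Report parenteral antibiotic use by arm. Prespecify a sensitivity analysis that scores parenteral rescue as non-favorable, and say what counts as rescue. Whether rescue is a failure in the primary analysis is for the sponsor to decide and state.

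The cost is wording in five places, CRF fields for antibiotic route, dates and reason (16.3 has the CRFs built after protocol finalization), one table and one sensitivity analysis. The downside is a lower favorable rate in both arms than under the literal rule, including among patients with chronic urinary symptoms (for example with indwelling catheters or neurogenic bladder) who may not fully resolve by day 28. The sensitivity analysis will depend partly on open-label decisions to use IV therapy.

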11.3.3. Statistical Analysis of the Primary Endpoint

The primary endpoint (percentage of patients exhibiting *favorable clinical outcomes*) will be evaluated for both arms of the study. A one-tailed, independent proportions Fisher's exact-test_will be used to compare the PCR test procedure against the conventional (C&S) diagnostic procedure; the following hypotheses serve as the basis for the test:

$$H_0: p_{PCR}^{FCl} \le p_{C\&S}^{FCl}$$

 $H_1: p_{PCR}^{FCl} > p_{C\&S}^{FCl}$

where FCl indicates favorable clinical outcome (primary endpoint) as defined in the earlier sections of this protocol, PCR represents the test procedure and C&S represents the conventional procedure. A 95% confidence interval will be calculated with the test statistic. A p-value of less than 0.05 will trigger the rejection of the null hypothesis.

Prior to statistical testing, a test for normality will be performed to ensure that the primary endpoint data from both treatment arms have a normal distribution and similar sample

UPH-STD-05-01 Version: 0

Effective Date: 06/23/2023 Page **29** of **44**

variance. If either condition is violated, a non-parametric test will be performed in replacement of the t-test.

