11. STATISTICAL EVALUATION

11.1. Sample Size

The sample size calculation was conducted using the software package G*Power (v3.1.9.7) on a two-group independent proportions Fisher's exact-test (one-tailed), chosen as the statistical test for the primary endpoint of this study. A type I (α) error probability of 0.05, and a power (1 – β) of probability 0.85 was chosen for the calculation; an allocation ratio of 1:1 was set to address the equally-sized treatment arms.

According to literature, patient populations that used C&S testing for cUTI management has a favorable clinical outcomes (FCl)percentage ranging from 60%-90% 8. For the purpose of this study, we assumed an FCl percentage of 75% for the C&S arm. A 10% expected improvement of the FCl in the PCR arm will require 574 enrolled participants. Assuming a 25% attrition rate & post-hoc exclusion rate (due to PCR or C&S negative result after randomization), up to 146 additional participants will be enrolled. Thus, up to 720 participants will be sufficient for

UPH-STD-05-01 Version: 0

Effective Date: 06/23/2023 Page **27** of **44**

Doc Lab Inc. / Protocol Number 22-UPHUV-01

Advarra IRB Approved Version 0, Date: 12 May 2023 / Pro00071764

completion of the study. The participants will be enrolled in at least 6 study sites (with an equal distribution of participants enrolled per site).

Exact - Proportions: Inequality, two independent groups (Fisher's exact test)

Options: Exact distribution

Analysis: A priori: Compute required sample size Input: Tail(s) = One Proportion p1 = 0.7 Proportion p2 = 0.8 α err prob = 0.05 Power (1- β err prob) = 0.85

Allocation ratio N2/N1 = 1

Output: Sample size group 1 = 287

Sample size group 2 = 287 Total sample size = 574

Actual power = 0.8513193Actual α = 0.0404397

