11.3.5. Exploratory Investigations

Exploratory data analysis will be conducted by stratifying the data by various factors, that include but are not limited to the following:

- Study Sites (minimum 6 with n = 120)
- Age: Elderly (\geq 65yrs) versus Non-Elderly (\leq 65yrs)
- Gender: Male versus Female
- Comorbidities: High Risk (reporting comorbidities) versus Low Risk (no reported comorbidities)

UPH-STD-05-01 Version: 0

Effective Date: 06/23/2023

• Pregnancy: Pregnant (positive for test) versus Non-Pregnant (negative for test or not applicable)

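### The pooled Fisher primary test spends only about 0.040 of its 0.05; an uncorrected site-stratified CMH test recovers about 2 points of power from the same patients

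*Combined protocol and SAP*

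**What the plan says.** - **Primary test (11.3.3).** A one-tailed "independent proportions Fisher's exact-test" of PCR against C&S, with no stratification or adjustment. The decision rule is "A p-value of less than 0.05 will trigger the rejection of the null hypothesis".
- **Sample size (11.1).** It was computed for the same test: "Input: Tail(s) = One Proportion p1 = 0.7 Proportion p2 = 0.8", "Allocation ratio N2/N1 = 1", target power "of probability 0.85 was chosen for the calculation". The output is "Total sample size = 574", with actual power 0.8513193 and actual alpha 0.0404397. The surrounding text instead assumes a C&S rate of 75% and a 10-point gain. Enrollment is raised to 720 to allow for 25% attrition and post-randomization exclusion.
- **Sites.** At least six, "with an equal distribution of participants enrolled per site" (11.1), about 120 each (2.1, 5.1). In the analysis, site appears only in the exploratory list of 11.3.5: "Study Sites (minimum 6 with n = 120".
- **Randomization (7.4).** Sequential enrollment numbers, odd or even, with no stratification by site stated.

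Section 11.3.3 also has a normality check with a fallback clause that mentions a t-test. That is a separate matter. I take Fisher's test as primary because 11.1 and the hypotheses in 11.3.3 both rest on it.

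**The concern.** An exact conditional test on two binomials cannot use all of its nominal error rate, and the protocol's own printout shows this: 0.0404 spent out of 0.05. The trial is also organised by site. Clinical outcome is assessed by site staff in an open-label design, so favorable-outcome rates may well differ between sites, and the pooled test makes no use of that structure.

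What is at stake is power, not validity. The plan needs 574 evaluable patients for 0.85, but 720 × 0.75 = 540, or 34 fewer. At the G*Power rates that shortfall puts the Fisher test below its target, and a gain of about 2 points is the size needed to get back.

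**Working it through.** **Inputs.** Rates 0.70 vs 0.80 (G*Power input) and 0.75 vs 0.85 (text of 11.1); one-sided 0.05; 287 per arm (11.1) and 270 per arm (540 / 2); six equal sites, so 270 / 6 = 45 per arm per site. Between-site spread is not in the documents and is assumed below.

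**1. Reproduce the plan's figures.** With n per arm and m total successes, Fisher rejects when P(X ≥ x₂ | m) ≤ 0.05, X hypergeometric(2n, m, n). Power is the sum of Bin(x₁; n, p₁) × Bin(x₂; n, p₂) over rejected tables. At n = 287:
- 0.70 vs 0.80: power 0.8513193, an exact match. At n = 286 it is 0.84997, so 287 is the correct minimum.
- Attained alpha 0.0404397 with both arms at 0.80, an exact match. With both arms at 0.70 or 0.75 it is about 0.041.

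**2. Alternatives.** Over sites k, with n₁ₖ and n₂ₖ patients per arm, Nₖ = n₁ₖ + n₂ₖ, and mₖ successes:

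z = Σ(x₂ₖ − mₖn₂ₖ/Nₖ) / √Σ[n₁ₖn₂ₖmₖ(Nₖ − mₖ) / (Nₖ²(Nₖ − 1))], reject if z ≥ 1.645.

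The continuity-corrected form subtracts 0.5 from the numerator. The unstratified pooled z-test separates the two sources of gain: Fisher to pooled z is the cost of conservatism, and pooled z to CMH is the effect of site.

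**3. Power at 270 per arm, 75% vs 85%.** Simulated with a constant odds ratio across sites. At 200,000 trials per cell the margin is about ±1.96 × √(0.9 × 0.1 / 200,000) = ±0.0013.

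| C&S site rates (assumed) | Fisher | Pooled z | CMH, uncorrected | CMH, corrected |
|---|---|---|---|---|
| all 75% | 0.880 | 0.900 | 0.900 | 0.880 |
| 65-85% | 0.883 | 0.902 | 0.905 | 0.885 |
| 60-90% | 0.886 | 0.905 | 0.912 | 0.892 |

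Fisher to pooled z: +2.0, +1.9, +1.9 points. Pooled z to uncorrected CMH: 0.0, +0.3, +0.7 points. With no effect (both arms averaging 75%), rejection rates in the three rows are 0.041, 0.039 and 0.037 for Fisher, about 0.050 for uncorrected CMH and about 0.040 for corrected CMH.

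**4. Power at 270 per arm, 70% vs 80%.** Exact enumeration gives Fisher 0.830 and pooled z 0.854. Uncorrected CMH gives about 0.854 with no site differences, 0.860 with C&S site rates of 60-80%, and 0.867 with 55-85%.

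**5. Boschloo's test (exact, unstratified), 270 per arm.** 0.848 at 70/80 and 0.893 at 75/85.

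**6. Sensitivity at 287 per arm, 70% vs 80%.**
- Site-logit SD 0, 0.25, 0.5 (C&S site rates all 0.70; 0.62-0.77; 0.54-0.84): uncorrected CMH 0.871, 0.875, 0.885 against Fisher 0.851, 0.853, 0.858, a gain of 2.0 to 2.7 points. At SD 0.75 and 1.0 (site rates as wide as 0.40-0.92) it is 3.5 and 4.3 points.
- Within-site arm counts left to chance, SD 0 to 0.5: CMH error 0.0496 to 0.0504 and gain over Fisher 1.8 to 3.0 points. Pooled Fisher's error is 0.041 to 0.042, so it is not inflated. At SD 0, CMH (0.8697) is slightly below pooled z (0.8722).
- Unequal sites (35% down to 5% of patients): CMH error 0.048 to 0.051, gain 1.8 to 2.8 points.

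**The case against.** The strongest reply is that nothing here is wrong. Fisher's test guarantees one-sided error at or below 5%, it is the test the sample size was computed for, and 11.1 discloses its attained alpha and still reaches 0.8513 at 287 per arm. At 75% vs 85% with 540 evaluable patients it has 0.880, above target. The 0.830 at 70% vs 80% arises from the attrition arithmetic and from the mismatch between the text rates and the G*Power rates, both separate issues. All of this stands, and it is why the point is one of efficiency only.

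Three stronger readings are tempting, and the documents do not support them.
- *That ignoring site is the main cause of the loss.* An unstratified pooled z-test recovers nearly the whole gain.
- *That the 60%-90% range in 11.1 shows how much sites differ.* It is a range from the literature on C&S-managed populations, not a spread between this trial's sites.
- *That within-site imbalance between arms harms the pooled test.* Exclusions could produce imbalance, but no bias or error inflation was shown, and letting arm counts vary by chance left Fisher's error near 0.041. Section 7.4 states no site stratification, so the analysis does not omit a design stratum.

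The remedy also depends on its wording. A continuity-corrected CMH test is as conservative as Fisher and gains almost nothing when sites are alike.

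**Conclusion.** The point holds as a cheap improvement. On the same patients, an uncorrected site-stratified CMH test gives about 2 points more power than pooled Fisher at about 5% one-sided error. At the G*Power rates with 540 evaluable patients, it moves power from 0.830 to 0.854, back to the stated 0.85.

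The 2-point part needs no assumption about sites. The further 0 to 0.7 point assumes site C&S rates spread by up to 15 points either side of the mean, with six equal sites and equal arms within site. Wider spreads would add more, but nothing in the documents establishes them. A reader might infer that the planned analysis is invalid or that its error rate is at risk; neither follows. The price of the gain is that error control becomes asymptotic: simulated 0.048 to 0.051 across the settings tried.

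**What to change.** Before any outcome data are seen, amend 11.3.3 to specify:
- a one-sided Cochran-Mantel-Haenszel test at 0.05, stratified by site, **without continuity correction**, as the primary test;
- a site-stratified (Mantel-Haenszel) risk difference with a matching interval. A one-sided 0.05 test corresponds to a one-sided 95% lower bound, which is the lower limit of a two-sided 1 − 2 × 0.05 = 90% interval. The section now promises a 95% interval without naming a method or side;
- a rule, fixed in advance, for combining sites too small to have patients in both arms;
- the pooled one-tailed Fisher test as a sensitivity analysis.

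If guaranteed error control without stratification is preferred, Boschloo's test is the alternative. It gains 1.8 points at 70/80 (0.830 to 0.848, just short of 0.85) and 1.3 points at 75/85 (0.880 to 0.893), both at 270 per arm.

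The cost is wording only, with no added patients, visits or data. Two downsides should be stated openly: error control is asymptotic, and the primary test no longer matches the G*Power printout. A sentence in 11.1 can cover the second, noting that 287 per arm was sized for Fisher (0.851) and gives about 0.871 under the new test with no site differences.
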